D	The number of days in the time interval considered for the derivation of seizure frequency
DEM	Data Evaluation Meeting
EQ-5D-5L	5-Level EuroQol-5 Dimension-Quality of Life Assessment
ES	Enrolled Set
FAS	Full Analysis Set
Gy	Gray
HLT	High Level Term
LCM	lacosamide
MDASI-BT	M.D. Anderson Symptom Inventory - Brain Tumor
MedDRA®	Medical Dictionary for Regulatory Activities
NIS	Non-interventional study
PGIC	Patient Global Impression of Change
PT	preferred term
QoL	quality of life
SAP	Statistical Analysis Plan
SEP	Submission excellence program
SOC	system organ class
SOP	Standard operating procedure
SD	standard deviation
SS	Safety Set
VAS	visual analogue scale

WHO	World Health Organization
WHO DD	World Health Organization Drug Dictionary

This document cannot be used to support any marketing authorization application and any extensions or variations thereof.
REDACTED COPY

1 INTRODUCTION

This document outlines the planned analyses to support the EP0045 clinical study report (CSR). It includes all definitions and details for the evaluation of data recorded during the study. This SAP should be read in conjunction with the non-interventional study observation plan dated 1 June 2015 and the annotated case report forms (aCRF) dated 31 August 2017.

2 PROTOCOL SUMMARY

2.1 Study objectives

2.1.1 Primary objective

The primary objective of this study is to evaluate the effectiveness and patient global impression of lacosamide (LCM) added to 1 or 2 antiepileptic drugs (AEDs) in the treatment of patients with brain tumor-related epilepsy (BTRE) due to low-grade primary brain tumor.

2.1.2 Secondary objective

The secondary objective of this study is to evaluate the tolerability and quality of life (QoL) of patients with BTRE due to low-grade primary brain tumor who are treated with LCM added to 1 or 2 AEDs.

2.2 Study variables

2.2.1 Efficacy variables

2.2.1.1 Primary efficacy variables

The following primary variables will be measured:

- Response at the end of the 6-month Observation Period, where a responder is a patient experiencing a 50% or greater reduction in partial-onset seizure frequency from Visit 1 (Baseline) to Visit 3 (Month 6 or end of Observation Period)
- Patient Global Impression of Change (PGIC) rating at Visit 3 (Month 6 or end of Observation Period)

2.2.1.2 Secondary efficacy variables

The following secondary variables will be measured:

- Retention on LCM at the end of the 6-month Observation Period
- Time to discontinuation of LCM treatment from the date of first dose of LCM
- Change from Visit 1 (Baseline) to Visit 3 (Month 6 or end of Observation Period) in the 5-Level EuroQol-5 Dimension Quality of Life Assessment (EQ-5D-5L) visual analogue scale (VAS) score and change in utility as converted from the 5 dimensions
- Change from Visit 1 (Baseline) to Visit 3 (Month 6 or end of Observation Period) in the M.D. Anderson Symptom Inventory - Brain Tumor (MDASI-BT)
- Actual change from Visit 1 (Baseline) to Visit 3 (Month 6 or end of Observation Period) in seizure frequency (seizures per 28 days)
- Percentage change from Baseline in seizure frequency

- Seizure-free status (Yes/No) at the end of the 6-month Observational Period
- Discontinuation rate of LCM due to adverse drug reactions (ADRs)
- Discontinuation rate of LCM due to lack of effectiveness
- Clinical Global Impression of Change (CGIC) rating at Visit 3 (Month 6 or end of Observation Period)

2.2.2 Pharmacokinetic/Pharmacodynamic variables

Not applicable

2.2.3 Safety variables

The following safety variables will be collected:

- Occurrence of ADRs or adverse events of special interest (AESIs) spontaneously reported by the patient or observed by the treating physician
- Patient withdrawal due to ADRs

2.3 Study design and conduct

EP0045 is a multicenter, prospective, single-arm non-interventional study (NIS) conducted at specialized sites utilizing LCM added to existing treatment with 1 or 2 AEDs in patients ≥ 16 years of age with BTRE secondary to low-grade tumor.

There are expected to be approximately 100 patients enrolled in the study (see Section 2.4) with 93 evaluable patients expected. Approximately 20 specialized centers are planned for participation. The expected recruitment period is 12 months. The Observation Period per patient will be up to 6 months after initiation of LCM treatment.

The patients will be followed as per current clinical practice for their condition. No additional diagnostic or monitoring procedures will be applied. The choices of AED treatment are made independently by the treating physician in the regular course of practice and are, therefore, independent of participation in this NIS.

The clinical evaluation of patients with BTRE secondary to low-grade tumor will be performed by the treating physician following routine clinical practice. All visits and assessments will be scheduled and conducted per routine clinical practice. It is anticipated that visits will occur every 3 months based on standard of care; therefore, each patient will have approximately 3 visits during their participation in this study. These visits will consist of:

- Visit 1, Baseline
- Visit 2, approximately 3 months after Baseline according to routine practice
- Visit 3, approximately 6 months after Baseline according to routine practice or end of Observation Period

Patients who discontinue early should perform Visit 3 assessments as a Withdrawal Visit.

At the Baseline Visit patient demographics, seizure frequency, and Baseline epilepsy medication will be documented. Assessment of Baseline seizure frequency will be assessed by retrospectively collecting seizure incidence during a period of 8 weeks prior to first LCM intake.

During the study seizure counts will be collected at each visit. At the last visit the patient's impression of change using the PGIC score will be recorded. The management and reporting of ADRs and AESIs will be handled according to international drug safety regulations and UCB procedures.

2.4 Determination of sample size

A sample size of 100 enrolled patients to obtain 93 evaluable patients was chosen for this study based on an expected 6-month responder rate (where a responder is a patient experiencing a 50% or greater reduction in partial onset seizure frequency from Visit 1 [Baseline] to Visit 3 [Month 6 or end of Observation Period]) of 60% with an expected precision in the 95% confidence interval (CI) of approximately $\pm 10\%$ for this estimate of response.

When the sample size is 93, a 2-sided 95% CI for a single proportion using the large sample normal approximation will extend 0.10 from the observed proportion for an expected proportion of 0.60.

Recruitment will be stopped at 100 enrolled patients and withdrawals will not be replaced.

3 DATA ANALYSIS CONSIDERATIONS

3.1 General presentation of summaries and analyses

All statistical analyses will be performed in an exploratory manner. Statistical analyses and generation of tables, figures, and listings will be performed using SAS version 9.1 or higher using validated program code according to relevant standard operating procedures. All tables and listings will use courier new font size 9.

A complete set of data listings containing both, documented data and all calculated data (eg, changes from Baseline) will be generated.

For continuous variables, summary statistics (number of available observations, mean, standard deviation (SD), minimum, lower quartile, median, upper quartile and maximum) will be tabulated. For categorical variables, frequency tables (number and percentages per category) will be presented. Unless otherwise specified the denominator for calculating percentages will be the number of patients in the respective population.

Unless otherwise noted, all percentages with the exception of 0 and 100 will be expressed to 1 decimal place, and 100% will be presented as integer. If a category has the frequency 0, the percentage value will be omitted. Mean and median changes from Baseline lower than the minimal displayable change will be displayed without sign (eg, -0.00 will be displayed as 0.00).

Decimal places for descriptive statistics will always apply the following rules:

- n will be an integer
- Mean, SD, and median will use 1 additional decimal place compared to the original data
- Minimum and maximum will have the same number of decimal places as the original value

3.2 General study level definitions

3.2.1 Analysis time points

The following visits are recommended documentation time points and will be considered for analysis. Due to the nature of a NIS, the time points given for each visit are approximated, expected time points only.

- Visit 1, Baseline
- Visit 2 (approximately 3 months after Baseline): Visits that occurred \leq 135 days after Visit 1
- Visit 3 (approximately 6 months after Baseline or Withdrawal Visit for patients who discontinue early): All visits that occurred $>$ 135 days after Visit 1

If there are 2 visits that meet the criteria for Visit 2, then the visit nearest to the scheduled assessment time for Visit 2 will be used (i.e. 90 days after Visit 1). If there are 2 visits that meet the criteria for Visit 3, then the visit nearest to the scheduled assessment time for Visit 3 will be used (i.e. 180 days after Visit 1). No different study periods will be considered for this NIS.

However, the period for the analysis of safety variables is defined as follows:

- Observational Period: The Observational Period starts with the start date of LCM and ends at the day of study termination. In case the start date of LCM is missing, the date of Visit 1 will be used instead.

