4 STUDY VARIABLES

4.1 Primary variables

The following primary variables will be measured:

- Response at the end of the 6-month Observation Period, where a responder is a patient experiencing a 50% or greater reduction in partial-onset seizure frequency from Visit 1 (Baseline) to Visit 3 (Month 6 or end of Observation Period)
- Patient Global Impression of Change (PGIC) rating at Visit 3 (Month 6 or end of Observation Period)

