15 RECOMMENDED SCHEDULE OF STUDY ASSESSMENTS

Table 15–1: Recommended schedule of study assessments

Assessments	Visit 1 ^a (Baseline)	Visit 2 Approximately 3 months after Baseline according to routine practice ^b	Visit 3 (End of Observation Period or Withdrawal Visit ^c) Approximately 6 months after Baseline according to routine practice ^b
Signed data consent	X		
Demographic data	X		
Medical history	X ^d		
Seizure history	X ^d		
Tumor diagnosis and grade (including review of most recent brain imaging results [CT or MRI])	X		X
Prior and concomitant tumor management (surgical procedures, chemotherapies, radiotherapy)	X ^d		X
Prior and concomitant AEDs	X	X	X
Other prior and concomitant epilepsy treatment	X	X	X
Other prior and concomitant relevant medications	X ^d	X	X
Verification of selection criteria	X		
Documentation of LCM administration	X	X	X
Documentation of seizure information (including seizure frequency and type) ^e		X	X
Karnofsky performance status	X	X	X
EQ-5D-5L	X		X

Table 15–1: Recommended schedule of study assessments

Assessments	Visit 1 ^a (Baseline)	Visit 2 Approximately 3 months after Baseline according to routine practice ^b	Visit 3 (End of Observation Period or Withdrawal Visit ^c) Approximately 6 months after Baseline according to routine practice ^b
MDASI-BT	X		X
PGIC			X
CGIC			X
Recording of ADRs and AESIs	X	X	X
Withdrawal criteria		X	X

ADR=adverse drug reactions; AED=antiepileptic drug; AESI=adverse event of special interest; CGIC=Clinical Global Impression of Change; CT=computerized tomography; EQ-5D-5L=5-Level EuroQol-5 Dimension Quality of Life Assessment; LCM=lacosamide; MRI=magnetic resonance imaging; MDASI-BT=M.D. Anderson Symptom Inventory - Brain Tumor; PGIC=Patient Global Impression of Change

^a Visit 1 will be performed after the decision is taken to start adjunctive LCM therapy. Treatment with LCM should be initiated according to routine clinical practice. If the first dose of LCM is given on the same day as Visit 1, it should be administered after Baseline assessments are complete. Previous treatment with LCM is allowed for up to 7 days prior to enrollment.

^b The frequency of visits after Visit 1 will be based on local clinical practice and the patients' requirements. The clinical procedures performed at each visit will also follow local clinical practice. It is estimated that patients will be followed at least every 3 months.

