3.10.5 Patient Global Impression of Change

Patients will be categorized based on their PGIC value collected at Visit 3 into the following groups:

- Improved: scores 1 to 3
- No change: score 4
- Worsened: score 5 to 7

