4.2 Handling of dropouts or missing data

All available data will be used for analysis.

Missing data of the variables will not be substituted. However, imputations of missing values as described in this section will be done in order to use the available data as much as possible, eg, imputations for missing or partial values for dates will be applied to calculate derived variables or to determine prior and concomitant medication

With respect to ADRs, events with missing information about action taken regarding UCB suspected drug status are regarded as ADRs leading to premature discontinuation. Events with no

answer to the question “Seriousness indicators: Is the event/reaction serious?” will be regarded as serious.

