8.1.2 Primary analysis of primary efficacy variables

8.1.2.1 Seizure frequency response

The number and percentage of responders, where a responder is a patient experiencing a 50% or greater reduction in partial onset seizure frequency from Visit 1 (Baseline) to Visit 3 (Month 6 or end of Observation Period), will be presented. The 95% CI for the percentage of responders will be calculated using the 2-sided Clopper-Pearson method.

Percentages are based on the number of patients with available data.

The seizure frequency response rate and corresponding 95% CI (2-sided Clopper-Pearson method) will be presented in each of the subgroups described in Section 4.8.

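### SAP 3.2.1 names early Withdrawal Visits as Visit 3, but its day rule sends those held by day 135 to Visit 2, and nothing says which prevails

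*SAP*

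**What the plan says.** **Visit windows.** In SAP 3.2.1 the Visit 3 bullet reads "Visit 3 (approximately 6 months after Baseline or Withdrawal Visit for patients who discontinue early): All visits that occurred" more than 135 days after Visit 1. The Visit 2 bullet takes visits at or before day 135 and makes no exception for Withdrawal Visits. If two visits qualify for Visit 2, "then the visit nearest to the scheduled assessment time for Visit 2 will be used", that time being day 90. For Visit 3 the target is day 180.

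**Early discontinuers.** SAP 2.3 says "Patients who discontinue early should perform Visit 3 assessments as a Withdrawal Visit". Protocol section 5 and Table 15-1 footnote c say the same, and the Visit 3 column of that table is headed "End of Observation Period or Withdrawal Visit". None of these sets a minimum day.

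**Primary variables.** Both are read at Visit 3. Protocol 4.1 gives the second as "Patient Global Impression of Change (PGIC) rating at Visit 3 (Month 6 or end of Observation Period", and the responder definition carries the same qualifier. SAP 3.10.5 adds: "Patients will be categorized based on their PGIC value collected at Visit 3 into the following groups".

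**Missing values and denominators.** SAP 4.2: "Missing data of the variables will not be substituted". SAP 8.1.2.1, and SAP 8.1.2.2 for PGIC: "Percentages are based on the number of patients with available data".

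**The concern.** A Withdrawal Visit on day 60 is Visit 3 by its label and Visit 2 by its date. Two programmers working from this SAP could therefore compute the responder percentage on different denominators. No formal testing is planned, so the descriptive percentages are the main result of the study and their denominators should not be open to choice.

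Under the day rule the patients affected are those seen for withdrawal by day 135 with no later visit. They are defined by an event after Baseline. Protocol 8.2 ties withdrawal to stopping LCM, to an increase in Baseline AED dose, or to needing more than 2 other AEDs, so there is no reason to expect them to be a random subset. Leaving them out changes the group that the percentage describes, and departs from the protocol definition while SAP 3.9 declares no such change.

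Seizure-free status depends on the Visit 3 seizure count and is affected in the same way. PGIC, CGIC and the EQ-5D-5L and MDASI-BT changes are affected too if Visit 3 means the analysis window and not the visit form.

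**Working it through.** **1. The plan's own figure.** Inputs from SAP 2.4: expected rate 0.60, half-width 0.10, two-sided 95% normal approximation. n = 1.96² × 0.60 × 0.40 / 0.10² = 92.2, rounded up to 93. The half-width at 93 is 1.96 × √(0.24/93) = 0.0996. The plan's 93 reproduces, and about 10 points is the yardstick for what follows.

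**2. Tracing patients through SAP 3.2.1.**

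- *Withdrawal Visit on day 60, no other visit.* By label it is Visit 3. By day rule it is Visit 2. The patient has a post-Baseline seizure assessment and is in the FAS under either reading (SAP 3.5.3), but under the day rule has no Visit 3 seizure frequency. With no substitution and available-data percentages, the patient leaves the responder numerator and denominator.
- *Routine visit on day 60, Withdrawal Visit on day 130.* Distances from day 90 are 30 and 40. The day rule keeps day 60, so the Withdrawal Visit is not used even as Visit 2.
- *Routine visit on day 140, Withdrawal Visit on day 160.* Both fall after day 135. Distances from day 180 are 40 and 20, so day 160 is used. There is no conflict here, but a correction must not disturb this case.

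**3. What a difference could look like.** The documents give no count of early Withdrawal Visits and no outcomes, so every input here is assumed: FAS 93, 10 patients with a Withdrawal Visit by day 135 and no later visit, 50 responders among the other 83, all of whom have Visit 3 data. Under the day rule the rate is 50/83 = 60.2% (Clopper-Pearson 95% CI 48.9 to 70.8). With the Withdrawal Visit as Visit 3:

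| Responders among the 10 | Rate | Difference from day rule |
|---|---|---|
| 0 | 50/93 = 53.8% | -6.5 points |
| 4 | 54/93 = 58.1% | -2.2 points |
| 6 | 56/93 = 60.2% | 0.0 points |
| 8 | 58/93 = 62.4% | +2.1 points |

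Varying the assumed number, with none of these patients responding: 5 patients give 53/88 = 60.2% against 53/93 = 57.0%; 20 give 44/73 = 60.3% against 44/93 = 47.3%. The planning half-width at 83 patients is 1.96 × √(0.24/83) = 10.5 points, so the loss of precision is small. What matters is which patients are counted.

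**4. A separate property of the protocol reading.** Post-Baseline frequency is computed over the days since the previous visit (SAP 3.10.4), which can be few for a Withdrawal Visit. Assume Poisson counts at an unchanged Baseline rate. With 1 seizure in 56 Baseline days (the minimum in protocol 8.1) and an interval D under 112 days, only a zero count is a response, with probability exp(-D/56): 78% for D = 14 and 61% for D = 28. With 6 seizures in 56 days the chance of response is 22% over 14 days (mean 1.5, zero needed) and 20% over 28 (mean 3, at most 1). The effect is large at low Baseline rates and much smaller at higher ones.

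**The case against.** The best defence is that the documents as a whole point one way. Protocol 4.1, section 5 and Table 15-1, and SAP 2.3, all place Visit 3 assessments at withdrawal. SAP 3.2.2 ends observation at the Withdrawal Visit for those who discontinue, and its fallback applies only to patients with no Visit 3, so it treats the Withdrawal Visit as Visit 3. SAP 3.9 reports no departure from the protocol. A careful programmer would probably follow the label. This stands: the two readings are not equally supported. It does not remove the problem, because the only rule that can be programmed directly says otherwise and nothing subordinates it. SAP section 4 uses withdrawn patients' data as far as their last visit, but does not say under which visit label.

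Two limits on the consequence also stand:

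- PGIC is scheduled only at Visit 3 or withdrawal, so the SAP 3.10.5 wording may naturally mean the form used. Its loss is less certain than that of the responder status.
- FAS membership does not change, and early withdrawals stay visible in disposition, retention, discontinuation and the listings.

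A reader might infer that the day rule inflates the responder rate. The documents do not support that, since the early withdrawals' outcomes are not given and the illustration runs in both directions. A reader might also infer that any patient without a Withdrawal Visit lacks Visit 3 data. That is wrong for completers and for anyone with a routine visit after day 135; it holds only for withdrawn patients with no visit after day 135.

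Finally, chance response over short intervals is a separate matter that arises under the protocol reading. It is no argument for the day rule.

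**Conclusion.** The contradiction is in the current text of SAP 3.2.1 and should be settled before database lock. It is more than missing detail: the day rule, followed literally, gives a result at odds with the protocol's definition of the primary variables.

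The firm consequence is for the responder percentage and seizure-free status of FAS patients whose Withdrawal Visit falls by day 135 and who have no later visit. For PGIC, CGIC, EQ-5D-5L and MDASI-BT it depends on how Visit 3 is read. The trigger is the date of the Withdrawal Visit, not the date of withdrawal.

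Size and direction cannot be stated. The differences of -6.5 to +2.1 points rest on the assumed 10 patients, the assumed 50 of 83, and the chosen splits. They show only that the choice could matter against a planned precision of about 10 points. The documents do not support a claim that the SAP is neutral between the readings, that the analysis set changes, or that both primary summaries necessarily lose patients.

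**What to change.** 1. In SAP 3.2.1, state that a Withdrawal Visit is always analysed as Visit 3, whatever its day, and takes precedence over any other visit after day 135 for that patient. State that the day-135 windows and the nearest-visit rules apply only to the remaining visits. The precedence clause is needed: without it, a patient with a routine visit on day 140 and a Withdrawal Visit on day 160 would have two Visit 3 candidates and no rule to choose between them.
2. Beside the primary responder and PGIC percentages, report how many Visit 3 values come from Withdrawal Visits by day 135.
3. Optional, and not needed to resolve the contradiction: in SAP 8.1.2.1 add one sensitivity display of the responder percentage over all FAS patients, counting early withdrawals and missing Visit 3 data as non-responders. Early withdrawals can be identified from the premature-termination record already summarised in SAP 5.1. In the illustration this gives 50/93 = 53.8% whatever the outcomes of the 10, by construction.

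The cost is SAP wording and minor programming on data already collected. Compared with the day-rule reading, the primary percentage may move either way.

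### When Visit 2 falls after day 135 and the final visit lies further from day 180 than Visit 2, the tie-break in SAP 3.2.1 selects Visit 2 as Visit 3 and leaves the completed final-visit PGIC unused.

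*SAP*

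**What the plan says.** SAP 3.2.1 puts visits up to and including day 135 after Visit 1 into Visit 2. Visit 3 is "All visits that occurred $>$ 135 days after Visit 1". For duplicates it says "If there are 2 visits that meet the criteria for Visit 3, then the visit nearest to the scheduled assessment time for Visit 3" is used, and it gives that time as day 180. The same section warns that "the time points given for each visit are approximated, expected time points only". SAP 2.3 expects 3-monthly visits ("It is anticipated that visits will occur every 3 months based on standard of care") and defines "Visit 3, approximately 6 months after Baseline according to routine practice or end of Observation Period".

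Protocol Table 15-1 marks PGIC and CGIC at Visit 3 only, and EQ-5D-5L and MDASI-BT at Visits 1 and 3. SAP 2.3 says the same of the last visit: there the patient's "impression of change using the PGIC score will be recorded". SAP 3.10.5 and 8.1.1.2 analyse the PGIC value from Visit 3.

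SAP 3.10.4 computes post-Baseline seizure frequency over the time since the previous visit. It defines both response and seizure-free status at Visit 3. Missing values are not substituted (SAP 4.2), and the percentages for PGIC and response use patients with available data (SAP 8.1.2).

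**The concern.** The schedule has only two post-Baseline visits, so two visits after day 135 normally means that the site's Visit 2 was late. The tie-break then compares distances to day 180. It does not ask which visit ended observation or which carries the questionnaires.

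If Visit 2 wins, a patient who completed the study with every form filled in has no PGIC at analysis Visit 3, although PGIC is a primary variable. CGIC and the changes in EQ-5D-5L and MDASI-BT are missing too, and the patient leaves the PGIC denominator. Response, the other primary variable, is still scored, but on the Visit 1 to Visit 2 interval. Seizures between Visit 2 and the end of observation are ignored for response and for seizure-free status. What is at stake is which visit defines the endpoint; precision hardly changes.

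**Working it through.** **Planned precision (SAP 2.4).** n = 0.60 × 0.40 × (1.96/0.10)² = 92.2, rounded up to 93. The half-width at n = 93 is 0.0996. The plan's figure is reproduced.

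**Condition for losing the final visit.** Let d2 be the day of a Visit 2 later than day 135, and d3 the day of the final visit. The rule keeps Visit 2 when |d2 − 180| < |d3 − 180|.

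- If d2 < 180, this means d3 > 360 − d2. Visit 2 on day 136 needs a final visit after day 224; day 140, after 220; day 150, after 210; day 160, after 200; day 170, after 190.
- If d2 is 180 or later, the final visit is always further away and is always dropped.

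**Examples.** Days 140 and 185 are 40 and 5 days from day 180, so the final visit is kept. Days 140 and 230 are 40 and 50 days away, so it is dropped.

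**Dependence on spacing.** Put d3 = d2 + g. For d2 < 180 the condition becomes d2 > 180 − g/2. With g = 90 this is d2 > 135, so every late Visit 2 displaces the final visit. With g = 60 it is d2 > 150. If the final visit is on day 180 exactly, no Visit 2 before that day displaces it.

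**How many patients.** The documents give no distribution of visit days, so this part rests on assumptions: Visit 2 normal with mean day 90, the same SD for both timings, and visits at least 14 days apart. In model A the final visit is centred on day 180 independently of Visit 2. In model B it follows Visit 2 by 90 days on average.

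| SD (days) | A: share of late-Visit-2 patients losing the final visit | A: expected of 93 | B: share | B: expected of 93 |
|---|---|---|---|---|
| 20 | 4% | 0.04 | 72% | 0.8 |
| 30 | 21% | 0.9 | 76% | 4.6 |
| 40 | 40% | 3.2 | 80% | 9.6 |

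With an SD of 15 days or less, fewer than 0.1 of 93 patients are affected under either model.

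**Effect on precision.** For an assumed PGIC proportion of 0.60, losing 2, 5 or 10 of 93 patients widens the half-width from 0.0996 to 0.1007, 0.1024 or 0.1054.

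**The case against.** The case for leaving the rule alone has several good parts.

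- Both documents place Visit 3 about 6 months after Baseline, not 3 months after Visit 2, and observation lasts up to 6 months. A final visit near day 180 is the one that the rule keeps. The protocol's expectation in the Table 15-1 footnote, "It is estimated that patients will be followed at least every 3 months", also makes a Visit 2 after day 135 an exception. This stands, and it is why the likely count is small. It does not remove the problem: SAP 3.2.1 sets no upper day limit, and it has a tie-break for two visits after day 135.
- A Visit 3 PGIC can be read as the one from the nominal visit in Table 15-1, and SAP 4.2 says all available data are used. On that reading PGIC survives. The SAP does not say so, and PGIC and response would then come from different visits. This stands as an ambiguity.
- Choosing the seizure record nearer Month 6 is a defensible window rule, since the variable is defined at Month 6 or end of observation. This stands for response taken alone. It does not justify preferring a visit without PGIC to one with it.
- Visit dates and all efficacy data are listed (SAP 5.1, 8.1), so an unused PGIC could be traced. This is true, but the summary tables would still omit it.

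A reader might infer that every patient with Visit 2 after day 135 loses the final visit. The documents do not support that: it needs the final visit to be further from day 180, and only a gap of 90 days or more guarantees this for every late Visit 2. Nor is the chance of a late Visit 2 the chance of a lost final visit. In model A at SD 30, about 4.8% of patients have a late Visit 2, but only about 1.0% lose the final visit.

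**Conclusion.** The point holds conditionally. Applied as written, the tie-break can replace the end-of-observation visit with a late Visit 2 that carries none of the final-visit questionnaires. Nothing in either document exempts those forms or gives the nominal Visit 3 priority. This goes beyond missing detail, because a stated rule can set aside a completed primary-variable form.

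The size is uncertain and probably small: about 0 to 3 of 93 patients if final visits centre on day 180, and about 1 to 10 if they follow Visit 2 by about 90 days. Both ranges assume visit-day SDs of 20 to 40 days, and the loss of PGIC assumes that the day window applies to questionnaires. In a descriptive single-arm study with no inferential analyses, severity is minor to moderate.

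**What to change.** In SAP 3.2.1, replace the Visit 3 tie-break with: *If two visits fall after day 135, the visit documented as Visit 3 / end of Observation Period (the one carrying the PGIC) is used as analysis Visit 3.* Add: *Questionnaires collected after Baseline only at the final visit are taken from the form on which they were recorded and are not removed by the day window.*

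The cost is this short SAP text and a line of code, with no new data; it should be settled before database lock. There are two side effects to accept knowingly. Some Visit 3 values will come from visits well after day 180; if the sponsor wants an upper limit, the SAP should state one. The second sentence also keeps questionnaires from Withdrawal Visits on or before day 135, which agrees with Protocol section 5, where early discontinuers complete the Visit 3 assessments.
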